## **Clinical trial registration**

Preregistered and published at clinicaltrials.gov with ID: NCT04522921 (initial release 13th August 2020).

**Document date:** 8th January 2021.

NB: As a result of the COVID-19 pandemic (impacting the study from December 2020 to February 2021), the study arms have been renamed in the protocol to enhance the clarity and interpretation of the study design and results.

## Background

Globally, the prevalence of childhood obesity has increased by ~50% from 1980 to 2013(1). In children and adolescents overweight and obesity are classified by an age-and- sex adjusted BMI. The World Health Organization (WHO) defines overweight by a BMI-SDS greater than 1 standard deviation (SD) and obesity by a BMI-SDS greater than 2 SD(2). This is equivalent to an ISO-BMI (ISO-BMI = the weight in kilograms divided by the height in meters squared) greater than or equal to  $25 \text{ kg/m}^2$  and greater than or equal to  $30 \text{ kg/m}^2$ (3). The most marked increase in childhood obesity has been observed in high-income countries, however, in the last part of the time-period a substantial increase has also been observed in middle- as well as low-income countries(1, 4). The Danish trends for childhood obesity are comparable to other high-income countries and in 2018, the Danish Health Authorities reported that 2.7% of children at age 7-13 years, 3.2% at age 14-15 years, and 3.9% at age 16-18 years were considered to be obese. For comparison, 16.8% of the adult Danish population is considered obese(5).

The development of childhood obesity is both complex and multifactorial depending on a combination of genetic/maternal, psychosocial, and environmental factors(6). Obesity in childhood and adolescence is highly predictive of continuous obesity into adulthood(7) and furthermore, associated with an increased risk of developing diseases such as type 2 diabetes (T2D), cardiac arrhythmias, premature stroke (age <55 years) and coronary heart disease (both non-fatal and fatal events) in adulthood as compared to never obese children(8-11). In addition, compared to their lean peers, children with obesity have in general lower self-esteem, more loneliness and a decreased quality of life (QoL), which is comparable to that of children with chronic diseases such as diabetes and cancer(12, 13).

Treatment or attenuation of obesity in children and adolescents can be obtained in various ways such as lifestyle interventions (i.e. changes in diet and physical activity), pharmacotherapy and bariatric surgery. As an adjunct to lifestyle intervention, pharmacotherapy could be an option, but only a few short-term (<6 months) studies have been performed. Recently, Liraglutide 3.0mg treatment for 7-13 weeks was found to significantly reduce BMI Z-score by  $-0.28$  in a population of 7-11 years old children with obesity ( $\text{isoBMI} > 30 \text{ kg/m}^2$ )(14). However, in the same study 37.5% vs. 12.5% in the placebo group experienced gastrointestinal side effects. Taking the possible adverse effects and the modest weight loss effects into account, these studies have had somewhat discouraging results and more long-term studies are needed(14, 15). Bariatric surgery is well-established as an obesity treatment in adults leading to weight loss and weight loss maintenance(16). Bariatric surgery is rarely performed in children and adolescents. In a study in adolescents with up to 5 years of follow-up, bariatric surgery was found to induce a weight reduction of 26%, comparable to the 29% found in adults(17). Despite comparable weight change 5 years after bariatric surgery, adolescents were significantly more likely to obtain remission of diabetes and hypertension as compared to adults, although both groups were still severely obese ( $\text{BMI} \sim 37 \text{ kg/m}^2$ ) at that time point(17). However, in the same study, the rate of reoperations and nutritional problems were significantly higher in the adolescents, a finding that is comparable to another study in which ~25% of the included young subjects (13-18 years of age) underwent additional abdominal surgery due to complications and ~70% displayed nutritional deficiencies(17, 18). Due to the invasive and somewhat discouraging results of pharmacotherapy and surgery in children and adolescents with obesity, lifestyle interventions seem to be a preferable and safe treatment option.

The literature on dietary intake and differences in macronutrient composition primarily comes from studies in adults. In adults, comprehensive studies in large cohorts have found that high intake of carbohydrates was associated with higher risk of total mortality and inversely, that higher intake of fruit, vegetable, legume, and dairy products was associated with a lower risk of total mortality(19-21). In line with the latter findings, total intake of fat as well as subtypes of fat (including saturated fat) was associated with lower risk of total mortality(19). In relation to carbohydrate intake it was recently suggested that the carbohydrate quality is of significant importance in relation to development of disease and there seem to be a dose-response relationship between the intake of dietary fiber, whole grain, and all-cause mortality as well as the development of non-communicable disease such as T2D, cardiovascular disease, and certain cancers (e.g. colorectal and breast cancer)(22, 23). In addition, intake of whole grain, fruit, and legume was reported to be inversely associated with the development of overweight and obesity in adults, and sugar-sweetened beverages to be the opposite, although the quality of evidence was low(24). In relation to weight loss and especially weight loss maintenance, protein, including dairy protein, seems at least in adults to be of importance(25). In children and adolescents, a recent systematic review found that caloric restriction down to a 50% reduction in estimated daily energy requirement resulted in a mean weight loss of ~10kg with a sustained weight loss of ~5kg after 5-14 months, with the most pronounced effect in adolescents (10-18 years)(26). Only two of the 24 studies included in this review reported on psychological well-being and found improvement in QoL. Only one of these reported on changes in eating behavior and found no effect on eating behavior(26). Few studies have investigated the effects of macronutrient composition in diets designed for weight loss in children and adolescents. Some report similar results on weight loss whether low carbohydrate or low fat was applied (27). Some report a beneficial effect of a high-protein/low carbohydrate diet compared to a low-fat diet on weight loss in severely obese children (28) and one recent meta-analysis found dairy products to be associated with a decreased risk of developing obesity in children(29). Other studies in children have reported conflicting results on supplementation with increased dietary protein as a way to obtain weight loss and/or reduce hunger when exposed to caloric restriction(30-32).

Dietary studies in children and adolescents on weight loss or weight loss maintenance combined with measures of QoL, including eating behavior and eating habits, are scarce. Therefore, the purpose of the present study is to perform a 10-week dietary intervention study with a follow-up after 52 weeks in children from 7-14 years of age with overweight or obesity in a multi-component overnight camp setting. In a caloric restricted and increased physical activity setting, the control group will consume a low-moderate protein diet (15 energy percent (E%)/day) whereas the intervention group will consume a higher protein diet (25E%/day).

## Aims

1. To test whether a diet with higher consumption of protein-containing foods is more favorable than the current weight-loss diet served to children and adolescents in the setting of a multi-component overnight camp (Julemærkehjem) on:
  - a. Anthropometry (BMI-SDS, fat-mass, fat-free masse)
  - b. Metabolic, inflammatory and liver markers.
  - c. QoL, eating behavior, eating habits and overeating/loss of control eating episodes.

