## **Recruitment/consent**

The camp staff manage the visitation of the children. At the first visit (pre-visit), which is an individual meeting at camp held behind closed doors with one of the camp staff, the parent/guardian will be asked to sign one written consent to participate themselves and one written consent for their child to participate. Furthermore, they will give oral consent if both parties want to participate in the trial.

We want to invite all the participating children and parents/guardians to a follow-up meeting 3 years, 5 years, 7 years and 10 years after the intervention to measure anthropometry and to answer questionnaires. Also a blood test will be collected from all participating children who voluntarily agrees to a blood test. When the children turn 18 years old, we will provide written and oral information to the adolescents and collect independent written and oral consent from the adolescent to continue to participate in the study.

Participants can be included if:

- The child start camp in Hobro or Fjordmark between October 2020 and March 2022.
- The child is between 7 and 14 years of age (inclusive) while attending camp.
- At least one parent/guardian submit written and oral consent to participate with his/her child.

- Parent/guardian has submitted oral and written consent to participation of their child. In case of shared custody both parents must submit oral and written consent to participation of their child. If one parent is not present at the first visit at camp, this parent must send a power of attorney with the other parent.

Participants will be excluded if:

- The child has a disease, diagnose or eating disorder that requires a special diet.
- The child or parent/guardian participate in another clinical trial or plan to do so in the near future.
- The parent/guardian do not understand the written informed consent.
- The child or parent/guardian are unwilling to or unable to comply with the study protocol and instruction given by the study staff.

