#### **Outcome measurements**

The primary outcome measure is BMI-SDS (35) which will be compared between the CG and the PG. BMI will be calculated ( $\text{kg}/\text{m}^2$ ) and weight categories defined using age- and sex-specific BMI-cut-offs from 2007 WHO references (35). Body weight (kg) and fat-free mass/fat-mass will be measured according to standard procedures by using a Bioelectric impedance (InBody model 270). Height (m) will be measured using a fixed wall measuring tape.

Teachers at the multicomponent overnight camps will be instructed how to measure anthropometrics and be responsible for measuring children. Children will be measured three times total; at baseline, 10-weeks and 52-weeks.

One participating parent/guardian will self-report their height and weight at baseline. All measurements are recorded to the nearest 0.1 kg and 0.1 cm.

Additionally, after resting in a chair, all children will have their blood pressure measured at baseline, 10-weeks and 52-weeks. Blood pressure will be measured with the right arm placed at heart level using an automatic non-invasive blood pressure monitor (Omron M3 model). Camp

staff will be instructed how to measure blood pressure correctly and note three measurements at each event from which an average will be calculated.

A blood test will be collected three times total; at baseline, 10 weeks and 52 weeks, from all participating children who voluntarily agrees to a blood test. The blood test will be collected to measure relevant metabolic-, inflammatory- and liver markers.

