## **Power calculation and statistics**

The power calculation was based on a previous study investigating the effect of a higher protein intake (21E% vs. 32E%) on childhood obesity (28). In this study, 22 and 24 children were allocated to the standard and high protein diet, respectively. Both groups had a reduction in BMI z-score during the 13-week intervention (from  $2.48 \pm 0.06$  BMI-z to  $2.10 \pm 0.10$  BMI-Z in the high protein group, and from  $2.51 \pm 0.05$  BMI-Z to  $2.40 \pm 0.10$  BMI-Z in the standard protein group), with a greater reduction in the high protein group ( $p = 0.03$ ). The number of participants needed to detect a between-group difference of  $-0.27$  SD with a power of 80% and a significance level of 5% was calculated to be  $\sim 55$  children in each group. Preferably, unadjusted mixed effects models will be performed to investigate differences in change between the groups.

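### Fat mass and fat-free mass have no growth-adjusted scale, so any difference in height growth between the two camps would appear as a diet effect

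*Combined protocol and SAP*

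**What the plan says.** Aims, item 1a, names the outcomes as "Anthropometry (BMI-SDS, fat-mass, fat-free masse", without a unit or scale for the last two.

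Outcome measurements makes BMI-SDS primary: "The primary outcome measure is BMI-SDS (35) which will be compared between the CG and the PG". On body composition it says "Body weight (kg) and fat-free mass/fat-mass will be measured according to standard procedures by using a Bioelectric impedance (InBody model 270". The kg in that sentence belongs to body weight. The only other unit information is "All measurements are recorded to the nearest 0.1 kg and 0.1 cm". Height is also taken: "Height (m) will be measured using a fixed wall measuring tape". On timing: "Children will be measured three times total; at baseline, 10-weeks and 52-weeks".

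Recruitment/consent sets the age range: "The child is between 7 and 14 years of age (inclusive) while attending camp". Study setup calls the trial non-randomised. Methods makes each diet arm a single camp: Fjordmark for the control group (CG) and Hobro for the protein group (PG).

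The only analysis sentence, in Power calculation and statistics, states a preference: "unadjusted mixed effects models will be performed to investigate differences in change between the groups". It gives no separate treatment for fat mass or fat-free mass, and no term for age, sex or height.

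**The concern.** Aim 1a tests the diet on three anthropometric outcomes. One is standardised for age and sex, and the other two are not standardised for anything. A growing child gains fat-free mass in kg, and fat mass in kg as well, even when body composition for height does not change. Change in mass over 52 weeks therefore contains growth as well as any effect of diet.

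Randomisation would balance growth between arms on average. Here nothing in the design does so, because each diet is one camp. Age, sex and pubertal mix drive growth and could differ between Hobro and Fjordmark. With an unadjusted model, nothing later in the analysis would remove such a difference. A PG-CG difference in fat-free mass could then be reported as an effect of protein when part of it is a difference in height growth.

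Leaving the scale open has a second cost. Kilograms, percentage fat and a height index can disagree in growing children, and the choice among them could be made after the data are seen.

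**Working it through.** **Inputs.** The documents give no mean or SD for fat mass, fat-free mass, height or growth, so the plan has no figure of its own to reproduce here. Its sample size of about 55 per group concerns BMI-SDS only. The values below are assumptions: start height h = 1.45 m, fat-free mass 32 kg, fat mass 20 kg, both masses scaling with height squared, and no change in composition for height.

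**Growth within a group.** Change in kg = baseline kg × [((h + g)/h)² − 1], for growth g over 52 weeks.

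| g | factor | fat-free mass | fat mass |
|---|---|---|---|
| 4 cm | 1.49²/1.45² = 1.056 | +1.79 kg | +1.12 kg |
| 5.5 cm | 1.505²/1.45² = 1.077 | +2.47 kg | +1.55 kg |
| 7 cm | 1.52²/1.45² = 1.099 | +3.16 kg | +1.98 kg |

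These amounts distort within-group change. If growth is equal in both camps they cancel in PG minus CG.

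**Difference in growth between camps.** Suppose mean growth is 6 cm in one camp and 5 cm in the other:

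- (1.51² − 1.50²)/1.45² = 0.0301/2.1025 = 0.0143
- Fat-free mass: 32 × 0.0143 = 0.46 kg
- Fat mass: 20 × 0.0143 = 0.29 kg

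**Range.** With start height 1.35 to 1.55 m, fat mass index 8 to 12 kg/m², fat-free mass index 14 to 16 kg/m² and 5 cm growth in the slower camp, the residual index × [(h + 0.05 + d)² − (h + 0.05)²] is:

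| difference d | fat-free mass | fat mass |
|---|---|---|
| 0.5 cm | 0.20–0.26 kg | 0.11–0.19 kg |
| 1 cm | 0.39–0.51 kg | 0.22–0.39 kg |
| 2 cm | 0.79–1.03 kg | 0.45–0.77 kg |

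**Ten weeks.** If 6 and 5 cm a year are spread evenly, heights at 10 weeks are 1.4615 and 1.4596 m (growth × 10/52). Then (1.4615² − 1.4596²)/1.45² is about 0.0027 (unrounded heights), which is about 0.09 kg fat-free mass and 0.05 kg fat mass. The growth problem is mainly one of the 52-week comparison.

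**Starting height.** With equal growth of 5 cm, a 5 cm difference in start height leaves only 0.04 to 0.08 kg over the same range of values. Through growth, it is the difference in growth that matters.

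**Proportional loss.** A separate mechanism is that larger children lose more kg for the same percentage loss. If fat mass differs by 3 kg and both camps lose 20%, change differs by 3 × 0.20 = 0.6 kg. At equal height of 1.45 m the index differs by 3/2.1025 = 1.43 kg/m², and 20% of that is 0.29 kg/m², so indexing does not help. If the gap is due to height alone (index 10 kg/m², heights 1.45 and 1.50 m, fat mass 21.0 and 22.5 kg), a 20% loss differs by about 0.3 kg in mass and by zero in the index. This is dependence on the baseline value, and it calls for a baseline term in the model.

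**The case against.** The strongest reply is that the plan never says the comparison will be made in kg. The 0.1 kg statement concerns recording precision, and BMI-SDS is itself built from measurements in kg and cm. That is correct. A reader might infer that a raw-kilogram analysis has been specified, but the documents support only that no scale is given and that the recorded masses are the default.

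Second, the planned contrast is a difference in change, so equal growth cancels. This stands. A reader might take the 1.8 to 3.2 kg of fat-free mass and 1.1 to 2.0 kg of fat mass as bias in PG minus CG. They are not; they bear on within-group change only. Nor does a difference in starting height matter much through growth.

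Third, nothing shows that the camps differ. Both take Danish schoolchildren under the same eligibility criteria, and the 1 cm gap is assumed. There is also no SD or target difference for these outcomes against which to judge 0.46 or 0.29 kg. This too stands, and it limits the point to an unprotected comparison, not a demonstrated bias.

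Fourth, the outcomes are not primary, the primary outcome is standardised, and Hypotheses does not name fat mass or fat-free mass. That lowers the priority. They are nevertheless named in Aim 1a as a test of the diet.

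Finally, an index removes height only, and kg adjusted for baseline value, age, sex and height would also serve. That is fair, and is why the fix adds model terms to the index.

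**Conclusion.** The concern holds in a limited form. Following the plan as written leaves any between-camp difference in mean height growth inside the PG-CG comparison of fat mass and fat-free mass, with neither the scale nor the model to remove it. On the assumed child, the size at 52 weeks is about 0.46 kg fat-free mass and 0.29 kg fat mass per 1 cm difference in growth. Over the wider assumed range it is 0.39 to 0.51 kg and 0.22 to 0.39 kg. All of this rests on assumed body sizes, on mass scaling with height squared, and on a growth difference for which the documents offer no evidence either way. The BMI-SDS comparison is not affected by this point. The change is worth making because the better scale can be had from data already planned.

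**What to change.** In Aims (1a) and Outcome measurements, define the body-composition outcomes as fat mass index and fat-free mass index: mass in kg divided by the square of height in m at the same visit. State that these are the PG-CG comparison at 10 and 52 weeks.

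In Power calculation and statistics, state that the model for these outcomes includes the baseline value, age and sex, because indexing deals with height only. Raw kg may be reported alongside, with a note that within-group change in kg includes growth.

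The cost is wording. Height and the impedance masses are already due at all three visits, and age and sex are already needed to compute BMI-SDS. What remains after the change is confounding of diet with camp, including pubertal timing not captured by age and sex. That should be stated as a limitation.

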## **Hypotheses**

Compared to the current weight-loss diet, we hypothesize that a diet with higher consumption of protein-containing foods will more effectively induce weight loss (a reduction in BMI-SDS) or weight maintenance in children with overweight or obesity, and improve risk factors for type 2 diabetes. Furthermore, we hypothesize that QoL will improve during the intervention and in relation to weight loss.

## **Study setup**

The COPE-study is a non-randomized trial and a collaboration with the staff of the multi-component-overnight camps (Julemærkehjem) in Denmark. The multi-component-overnight camps are well-established intensive weight loss camps to which Danish schoolchildren, from 7-14 years of age, are referred to for 10-weeks intervention focusing on a healthy lifestyle, healthy eating, new habits and increased physical activity.

## **Participants**

A total of 350 children attending a multi-component overnight camp in Hobro and Fjordmark for 10 weeks will be invited to participate in the study. The capacity is 48 children in camp Hobro and 30 children at camp Fjordmark, and every 2nd or 3rd week new children start camp in groups of 8-12 children. Annually, 240 children attend camp Hobro and 150 children attend camp Fjordmark.

Parent/guardian will be co-participants and help their child answer questionnaires. One time, in the initial period of the study, parent/guardian will be asked to report their weight (kg) and height (m) and parents will be asked health-related and family-related questions. Furthermore, at least one parent/guardian will participate in the nutrition education class at the multi-component-overnight camp with their child.

## **Recruitment/consent**

The camp staff manage the visitation of the children. At the first visit (pre-visit), which is an individual meeting at camp held behind closed doors with one of the camp staff, the parent/guardian will be asked to sign one written consent to participate themselves and one written consent for their child to participate. Furthermore, they will give oral consent if both parties want to participate in the trial.

We want to invite all the participating children and parents/guardians to a follow-up meeting 3 years, 5 years, 7 years and 10 years after the intervention to measure anthropometry and to answer questionnaires. Also a blood test will be collected from all participating children who voluntarily agrees to a blood test. When the children turn 18 years old, we will provide written and oral information to the adolescents and collect independent written and oral consent from the adolescent to continue to participate in the study.

Participants can be included if:

- The child start camp in Hobro or Fjordmark between October 2020 and March 2022.
- The child is between 7 and 14 years of age (inclusive) while attending camp.
- At least one parent/guardian submit written and oral consent to participate with his/her child.

- Parent/guardian has submitted oral and written consent to participation of their child. In case of shared custody both parents must submit oral and written consent to participation of their child. If one parent is not present at the first visit at camp, this parent must send a power of attorney with the other parent.

Participants will be excluded if:

- The child has a disease, diagnose or eating disorder that requires a special diet.
- The child or parent/guardian participate in another clinical trial or plan to do so in the near future.
- The parent/guardian do not understand the written informed consent.
- The child or parent/guardian are unwilling to or unable to comply with the study protocol and instruction given by the study staff.

